#### 8.1 Inclusion Criteria

Written informed consent must be obtained before any study specific assessment is performed. Upon signing informed consent, the subject is considered enrolled in the study.

Subjects eligible for inclusion in this study must fulfill all of the following criteria:

- 1. Subject must be able to understand and sign an IRB/IEC approved Informed Consent form.
- 2. Willing and able to attend all scheduled study visits as required per protocol.
- 3. Subjects must be  $\geq 38$  and  $\leq 58$  years of age.
- 4. Current contact lens wearers (during the past 3 months for a minimum of 5 days per week and 6 hours per day) of any MF contact lens (with a preference for Alcon

TDOC-0055656 Effective

Page 32 of 59

Precision Profile Design wearers) with a LO or MED ADD (or equivalent to an ADD of max +2.00 D).

OR

Current PAL wearers (wearing spectacles for a minimum of 5 days per week and 6 hours per day) with a prescription check in the last 12 months and spectacles up to date based on the prescription check with an ADD no higher than +2.00 D and a spherical refractive error between -0.50 and -6.50 D.

- 5. Contact lens wearers: manifest cylinder (at screening) less than or equal to 0.75 D in each eye and a spherical refractive error (vertex distance 10-14mm) between -0.50 and -6.50 D
- 6. Subjects' BCVA vision with manifest refraction must be 0.1 (logMAR) or better in each eye at distance at Visit 2.
- 7. Willing to discontinue artificial tears and rewetting drops within approximately 2 hours prior to or during study Visit 2.

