Subject population	Presbyopic subjects aged $\geq 38$ and $\leq 58$ years with normal eyes (other than correction for refractive error), whose habitual correction is either any MF contact lens (with a preference for Alcon Precision Profile Design wearers) with a LO or MED ADD (or equivalent to an ADD of max +2.00 D) or progressive addition lens spectacles. Wear of habitual correction must be at least 5 days per week and at least 6 hours per day.
	Planned number of subjects enrolled: ~ 60
	Required number of completed subjects: 48 (12 per group)
Key inclusion	Presbyopic subjects aged $\geq 38$ and $\leq 58$ years with normal eyes
criteria	(other than correction for refractive error), whose habitual
(See Section 8.1 for a	correction is either any MF contact lens (with a preference for
complete list of	Alcon Precision Profile Design wearers) with a LO or MED ADD
inclusion criteria)	(or equivalent to an ADD of max +2.00 D) or progressive addition
	lens spectacles. Wear of habitual correction must be at least 5 days
	per week and at least 6 hours per day.
Key exclusion	Monocular subjects or subjects fit with only one contact lens.
criteria	Known pregnancy or lactating. History of or planned refractive
(See Section 8.2 for a	surgery or irregular cornea in either eye.
complete list of	
exclusion criteria)	
· 	

TDOC-0055656 Effective

Page 17 of 59

Data analysis and	Planned Analysis	Planned Analysis			
sample size justification	To address the primary effectiveness objective, planned analysi summarized below:				analysis is
	Endpoint	Comparison	Statistica	al Method	
	Primary				
	Average transition time between distance and intermediate	MF lenses vs PALs		ized linear in = 0.5 se	
	No inferential testin	ng will be perfor	med for th	e safety aı	nalyses.
	Sample Size Justification				
Sample size calculation for the primary effectiveness expression (one-sided $\alpha = 0.05$ ) is summarized below:					dpoint
	Primary Endpoint	Assumptions		Power	N/group
	Average transition time between distance and intermediate	Common SD  NI margin =		80%	12
Key words	Presbyopic, multifocal				
Associated materials	Lubrication/re-wetting drops will not be permitted within 2 hours prior to study Visit 2.				

Page 18 of 59

Table 3–1 Schedule of Study Procedures and Assessments

	ALL SUBJECTS	MULTIFOCAL CONTACT LENS WEARERS	PROGRESSIVE ADDITION LENS SPECTACLE WEARERS	ALL SUBJECTS
Visit	Visit 1/	Visit 2/	Visit 2/	Unscheduled

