#### 7 INVESTIGATIONAL PLAN

## 7.1 Study Design

This is a prospective, randomized parallel group study measuring the average transition time

[figure not shown]
Habitual contact lens wearers will be randomized to either AOHG MF, DACP MF, or DT1 MF contact lenses. This will be a double-masked trial for the contact lens group. The PAL wearers will not be randomized and will wear their habitual PALs during the study. This group will not be masked. Investigators will be masked to the brand and type of PAL for habitual PAL wearers.

2.0; Most-Recent; Effective; CURRENT
Page 30 of 59

Subjects will be expected to attend 1 to 2 office visits (Visit 2 may be performed on the same day immediately following Visit 1). All study contact lenses will be prescribed according to the subject's prescription and fitted using the Alcon MF fitting guide. PAL wearers will wear their habitual spectacles. Subjects are expected to complete the study in approximately 2 to 3 hours.

The study is expected to be completed in approximately 8 weeks.

Figure 7-1 Study Design

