#### Table 9–2 **Control Product**

Control Product(s)	Progressive addition lens spectacles
Manufacturer	N/A
Indication for Use	Subjects will use their habitual progressive addition lens spectacles
	as instructed by their eye care professional.

2.0; Most-Recent; Effective; CURRENT

Page 36 of 59

Product description	Progressive addition lens spectacles
and parameters	
available for this	
study	
Formulation	N/A
Usage	N/A
Number/Amount of	N/A
Product to be	
Provided to the	
subject	
Packaging	N/A
description	
Labeling description	N/A
Storage conditions	N/A
Additional	N/A
identifying	
information	
Supply	Subject will provide their own habitual progressive addition spectacles

The study lenses must be maintained within specified environmental condition, per the labeling.

More information on the test products can be found in the Package Inserts, Directions for Use.

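### Inclusion criterion 4 sets a 3-month look-back for multifocal contact lens wearers but none for PAL wearers, so recent first-time PAL wearers are not clearly kept out of the non-randomized control group

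*Protocol*

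**What the plan says.** Criterion 4 in Protocol section 8.1 has two branches joined by OR. The contact lens branch reads "Current contact lens wearers (during the past 3 months for a minimum of 5 days per week and 6 hours per day", and accepts any MF lens with a low or medium add. The PAL branch reads "Current PAL wearers (wearing spectacles for a minimum of 5 days per week and 6 hours per day) with a prescription check". Its only element of time is a "prescription check in the last 12 months and spectacles up to date based on the prescription check".

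The Protocol Summary describes the population by habitual correction, either MF lenses or PALs, and adds "Wear of habitual correction must be at least 5 days per week and at least 6 hours per day". SAP Table 1-1 repeats this. Protocol section 7.1 states "The PAL wearers will not be randomized and will wear their habitual PALs during the study", and Table 9–2 says of the control "Subjects will use their habitual progressive addition lens spectacles". None of these places says how long a correction must have been worn to count as habitual, and no exclusion criterion in section 8.2 deals with recent first PAL wear.

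The target is 12 completers per group. The primary comparison pools the three MF groups against PAL. The only model term stated is treatment (Protocol section 12.4.1.2; SAP section 4.3.1).

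**The concern.** The plan asks for established wear on one side of the comparison and not on the other, and gives no reason for the difference. PAL subjects are not randomized, so eligibility criteria are the main visible protection for comparability with the MF group.

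The endpoint is the time to switch between 4 m and 80 cm. It is reasonable to suppose, though the documents do not say so, that a person new to PALs takes longer to find the right part of the lens. Such subjects would lengthen the PAL mean and so lower MF minus PAL. That moves the upper confidence limit (UCL) toward the noninferiority criterion (below 0.5 s) and toward the follow-on superiority criterion (below 0), for a reason unrelated to the contact lenses. With 12 control subjects, a few could move the mean noticeably.

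**Working it through.** **1. The two branches side by side**

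| Element | MF branch | PAL branch |
|---|---|---|
| Schedule | 5 days/week, 6 h/day | 5 days/week, 6 h/day |
| Look-back for the schedule | past 3 months | none stated |
| What is worn | any MF contact lens | spectacles |
| Other time limit | none | prescription check within 12 months, spectacles up to date |

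The 12-month check limits how old the prescription may be. It does not limit how recently the PALs were dispensed.

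**2. Inputs**

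- From Protocol section 12.8 and SAP section 7: SD 0.456 s, margin 0.5 s, one-sided alpha 0.05, 12 per group, hence 36:12 for pooled MF against PAL.
- Assumed, not in the documents: k of the 12 PAL subjects are new to PALs, and each is slowed by d seconds.
- The SD is taken to apply to each subject's average transition time.

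**3. The plan's own figures**

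Power comes from the noncentral t with noncentrality (0 − 0.5)/SE, where SE = 0.456 × √(1/n_MF + 1/n_PAL) and the true difference is taken as 0.

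- 11 per group gives 79.9% and 12 per group gives 83.1%, so 12 is the smallest 1:1 size reaching 80%.
- 21:7 gives 78.9% and 24:8 gives 83.6%, so 24:8 is the smallest 3:1 size reaching 80%.

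Both stated sample sizes reproduce. At the planned 36:12, SE = 0.456 × √(1/36 + 1/12) = 0.152 s and power is about 94%.

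**4. Effect of slower control subjects**

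Shift in the PAL mean = k × d / 12. For k = 3:

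- d = 0.25 s: 3 × 0.25 / 12 = 0.0625 s, or 12.5% of the margin
- d = 0.5 s: 3 × 0.5 / 12 = 0.125 s, or 25% of the margin
- d = 1.0 s: 3 × 1.0 / 12 = 0.25 s, or 50% of the margin

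The false noninferiority rate was simulated with 36 MF and 12 PAL subjects, SD 0.456 and a true difference of exactly 0.5 s among adapted wearers. Noninferiority is declared when the one-sided 95% UCL is below 0.5. The simulation includes the extra spread that the slowed subjects add to the control group.

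| PAL subjects slowed | d (s) | Shift (s) | False noninferiority |
|---|---|---|---|
| 0 of 12 | – | 0 | 5.0% |
| 1 of 12 | 0.25 | 0.021 | 6.5% |
| 1 of 12 | 0.5 | 0.042 | 8% |
| 1 of 12 | 1.0 | 0.083 | 12% |
| 3 of 12 | 0.25 | 0.0625 | 10.5% |
| 3 of 12 | 0.5 | 0.125 | 19% |
| 3 of 12 | 1.0 | 0.25 | 41–42% |

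The last entry is 41.4% with the residual variance taken within four groups (44 df), and 42.0% with a two-group pooled variance.

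**The case against.** The strongest case against has four parts.

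- **The control is described as habitual.** The Protocol Summary ties the 5-day, 6-hour minimum to the habitual correction, and someone given a first PAL last week is hard to call a habitual PAL wearer. This stands in part. A reader might infer from criterion 4 that PAL wearers face no wear requirement at all, or that single-vision wear would satisfy it. The summary does not support that reading. What is missing is a number: habitual is never given a duration for PAL wearers, and an investigator could reasonably apply it either way.
- **The mechanism and its size are assumed.** This stands. The documents do not say that new PAL wearers are slower, by how much, or how many would enrol. A delay of 0.5 to 1.0 s is one to two whole margins and 1.1 to 2.2 SDs (0.5/0.456 and 1.0/0.456). With one subject slowed by 0.25 s, the error rate barely moves.
- **There may be an opposing bias.** MF subjects may come from any MF brand and are tested in a newly fitted study lens worn for up to 3 hours, while PAL subjects use their own spectacles. Unfamiliarity on the MF side would work against noninferiority. This stands, so the net direction cannot be settled. It does not close the gap, because an unmeasured opposing bias is not a control.
- **Wear time may be collected.** The visible schedule row for habitual correction lists type or brand and power only. However, other rows are redacted, the SAP text on baseline factors (listed in its contents as section 4.5) is not visible, and procedures sit in the manual of procedures. A reader might infer that wear time could never be adjusted for; the documents do not allow that conclusion.

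A reader might also see the 0.75 D cylinder limit in criterion 5, which applies to contact lens wearers only, as a second bias of the same kind. That does not follow. Table 9–1 lists sphere power and add for the study lenses and no cylinder power, so a limit for lens wearers has an obvious fitting reason. Nothing in the documents indicates that astigmatic PAL wearers would switch more slowly.

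**Conclusion.** The gap is real and narrow. Criterion 4 gives MF wearers a 3-month look-back and gives PAL wearers none, and no other provision in the protocol or SAP supplies one. Recent first-time PAL wearers are therefore not clearly excluded from a non-randomized control group of 12.

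Taken alone, this opens a route of bias toward noninferiority if new PAL wearers are slower. The size is unknown. The illustrative false noninferiority rates of about 10%, 19% and 41–42% rest on an assumed 3 of 12 affected subjects and assumed delays of 0.25, 0.5 and 1.0 s. They show sensitivity and are not predicted error rates. A reader might take them to mean that the trial as a whole is tilted toward noninferiority; the newly fitted MF lens may pull the other way, so the documents do not support that. The sample size is unaffected.

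**What to change.** Make the PAL branch of criterion 4 parallel to the contact lens branch. Insert the same 3-month look-back before the 5-day, 6-hour schedule, and have the schedule refer to wearing PALs instead of spectacles. Leave the prescription-check clause as it is. Do not require 3 months in the same pair: the MF branch accepts any MF lens, so that would create a new imbalance and exclude established PAL wearers who recently updated their spectacles. Criterion 5 needs no change on this account.

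Record the duration of wear of the habitual correction in both groups, if it is not already collected, so that the balance can be shown.

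The cost is one phrase in one criterion and at most one extra data field. A few very recent PAL wearers would be screened out of a group that needs 12 completers. The target of 48 completers does not change.

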#### 8.2 Exclusion Criteria

Subjects fulfilling any of the following criteria are not eligible for participation in this study.

- 1. Any anterior segment infection, inflammation, or abnormality or disease (including systemic) that contraindicates contact lens wear, as determined by the Investigator
- 2. Any use of systemic or ocular medications for which contact lens wear could be contraindicated, as determined by the Investigator.
- 3. History of refractive surgery or plan to have refractive surgery during the study or irregular cornea in either eye.
- 4. Ocular or intraocular surgery (excluding placement of punctal plugs) within the previous 12 months or planned during the study.
- 5. Biomicroscopy findings at screening that are moderate (Grade 3) or higher and/or corneal vascularization that is mild (Grade 2) or higher, and/or any infiltrate.

TDOC-0055656 2.0; Most-Recent; Effective

Page 33 of 59

- 6. Current or history of pathologically dry eye in either eye that, in the opinion of the Investigator, would preclude contact lens wear.
- 7. Current or history of herpetic keratitis in either eye.
- 8. Eye injury in either eye within 12 weeks immediately prior to enrollment for this trial.
- 9. Current or history of intolerance, hypersensitivity or allergy to any component of the study products.
- 10. Any use of topical ocular medications and artificial tear or rewetting drops that would require instillation during contact lens wear.
- 11. The Investigator, his/her staff, family members of the Investigator, family members of the Investigator's staff, or individuals living in the households of the aforementioned persons may not participate in the study.
- 12. Participation of the subject in a clinical trial within the previous 30 days or currently enrolled in any clinical trial.
- 13. Monocular subjects (only one eye with functional vision) or subjects fit with only one contact lens.
- 14. Known pregnancy or lactating.

## 8.3 Rescreening of Subjects

Rescreening of subjects is not allowed in this study.

#### 9 TREATMENTS ADMINISTERED

## 9.1 Investigational Product(s)

*Test Product(s):* 

- AIR OPTIX plus HydraGlyde (lotrafilcon B) Multifocal (AOHG MF) contact lens
- DAILIES TOTAL1 (delefilcon A) Multifocal (DT1 MF) contact lens
- DAILIES AquaComfort Plus (nelfilcon A) Multifocal (DACP MF) contact lens

Control Product(s) (If applicable): Progressive addition lens spectacles

Page 34 of 59

Table 9–1 Test Products

Test Product	AIR OPTIX plus	DAILIES TOTAL1	DAILIES	
	HydraGlyde	(delefilcon A)	AquaComfort Plus	
	(lotrafilcon B)	Multifocal – DT1 MF	(nelfilcon A)	
	Multifocal – AOHG	contact lens	Multifocal – DACP	
	MF contact lens		MF contact lens	
) ( ) ( ) ( ) ( )	A1 Y 1 . Y Y			
Manufacturer	Alcon Laboratories, Inc.			
	[name]	4.2000		
	[name]	4-2099		
	USA			
Indication for				
use and				
intended	The intended use of thes	e contact lenses is for visi	on correction.	
purpose in the				
current study				
Product	Material: Lotrafilcon B	Material: Delefilcon A	Material: Nelfilcon A	
	Material: Lotranicon B	Material: Delenicon A	Material: Neifficon A	
description	Water content: 33%	Water content: 33%	Water content: 69%	
parameters		core, > 80% surface		
available for	Power range:		Power range:	
this study	-0.50 to -6.00 D in	Power range:	-0.50 to -6.00 D in	
tiiis staay	0.25 D steps	-0.50 to -6.00 D in	0.25 D steps	
	0.23 В зкерз	0.25 D steps	0.23 D steps	
	Add: LO, MED	0.20 B steps	Add: LO, MED	
		Add: LO, MED		
	Base curve (mm): 8.6	D ( ) 0.5	Base curve (mm): 8.7	
	mm	Base curve (mm): 8.5	mm	
	Diameter (mm): 14.2	mm	Diameter (mm): 14.0	
	mm	Diameter (mm): 14.1	mm	
		mm		
Formulation	Information can be found in the associated package insert			
Study Usage	Wear:	Wear:	Wear:	

Page 35 of 59

2.0; Most-Recent; Effective; CURRENT

TDOC-0055656 Effective

	Daily Wear	Daily Wear	Daily Wear		
	Bilateral	Bilateral	Bilateral		
	Replacement period:	Replacement period:	Replacement period:		
	N/A	N/A	N/A		
	Exposure:	Exposure:	Exposure:		
	approximately	approximately	approximately		
	2-3 hours	2-3 hours	2-3 hours		
	Lens Care: N/A	Lens Care: N/A	Lens Care: N/A		
Number/	One pair of study lenses	will be provided to each	subject in the contact		
Amount of	lens group according to their randomization assignment. Replacement				
product to be	lenses will be available if needed. Multiple lenses may be used to fit the				
provided to	subject per the Alcon M	F Fitting guide or investig	gator's discretion.		
the subject					
Packaging	Blister foil pack				
description					
Labeling	Commercial labeling				
description					
Storage	Refer to the package insert				
conditions					
Supply	Each Site will procure st	udy contact lenses. Refer	to the MOP,		
	Section 10.3, for additional details				

#### Table 9–2 **Control Product**

Control Product(s)	Progressive addition lens spectacles
Manufacturer	N/A
Indication for Use	Subjects will use their habitual progressive addition lens spectacles
	as instructed by their eye care professional.

2.0; Most-Recent; Effective; CURRENT

Page 36 of 59

Product description	Progressive addition lens spectacles
and parameters	
available for this	
study	
Formulation	N/A
Usage	N/A
Number/Amount of	N/A
Product to be	
Provided to the	
subject	
Packaging	N/A
description	
Labeling description	N/A
Storage conditions	N/A
Additional	N/A
identifying	
information	
Supply	Subject will provide their own habitual progressive addition spectacles

The study lenses must be maintained within specified environmental condition, per the labeling.

More information on the test products can be found in the Package Inserts, Directions for Use.

# 9.2 Other Medical Device or Medication Specified for Use During the Study

No other medical devices or medications are required to be used in conjunction with the treatments during the clinical study.

Page 37 of 59

# 9.3 Treatment Assignment / Randomization

Habitual contact lens wearing subjects will be randomized in a 1:1:1 ratio to receive AOHG MF, DT1 MF, or DACP MF, respectively. Habitual PALs wearing subjects will not be randomized.

Only after signing the ICF, a subject will be assigned a subject number by the electronic data capture system.

A randomization list will be generated using a validated system that automates the random assignment of treatment arms to randomization numbers in the specified ratio. Subjects will be assigned treatment according to the randomization list uploaded in the IRT system. The randomization list will be generated and maintained by the Study Sponsor.

At Visit 2, all eligible subjects in the contact lens group will be randomized via the EDC/IRT integration system to one of the treatment arms. The unmasked study coordinator will access the respective system after confirming that the subject meets all the eligibility criteria. A randomization number will be automatically assigned to the subject according to the subject randomization list but will not be communicated to the site user. The EDC/IRT integration system will inform the site user of the treatment assignment to be dispensed to the subject.

# 9.4 Treatment masking

The contact lens group in this study is double-masked, with contact lens group subjects randomized to use AOHG MF, DT1 MF or DACP MF lenses for the study visit. Investigators will be masked to the type and brand of PAL.

TDOC-0055656 Page 38 of 59 Effective

Table 9–3 **Unmasked Individuals Associated with the Study** 

Unmasked	Extent of Unmasking	Rationale
Individual		
Unmasked Study Coordinator(s)	The Unmasked Study Coordinator(s) will manage IP inventory, as well as IP administration. This individual will have access to IP supply, accountability logs, and other documents or supplies pertaining to IP (including brand/type of PAL). The unmasked coordinator will also assist with device deficiency and adverse event reporting.	The Unmasked Study Coordinator(s) will be unmasked to allow for storage and dispensing, as well as accountability for all contact lens IP.
Clinical Operations Lead (COL)	The COL will have access to IP supply, accountability logs, and other documents or supplies pertaining to IP. This individual assists with masked and unmasked data reviews.	The COL will be unmasked to allow for oversight of the CSM, in conjunction with all IP accountability tasks.
Clinical Site Manager (CSM)	CSM will have access to IP supply, accountability logs, and other documents or supplies pertaining to IP accountability. This individual monitors unmasked and masked study data.	The CSM will be unmasked to allow for performance of IP accountability, management of device deficiencies and related AE lens returns, and any other IP related tasks.
Unmasked Data Manager(s)	The Unmasked Data Manager(s) will have access to restricted fields in eDC that would contain unmasking data.	The Unmasked Data Manager(s) will be unmasked to allow for review of all restricted data.
IRT Manager	The IRT manager will be unmasked to allow for system programming,	The IRT manager is unmasked to all aspects of

Page 39 of 59

Unmasked	Extent of Unmasking	Rationale
Individual		
	testing, and to allow for technical oversight of the system.	the trial for system development purposes.
Randomization	The Randomization specialist will	Generates and therefore has
Specialist	be unmasked to allow for generation of the randomization list and	full knowledge of treatment codes but otherwise is
	uploading of that list into the IRT system.	operationally not associated with the Clinical Trial Team or any decision-making aspects related to clinical trial design, execution, or reporting.

This level of masking will be maintained throughout the conduct of the study. Unmasking will occur only after all planned study data have been validated, and the database locked.

Masked study personnel must avoid seeking information that may compromise masking. Unmasked study personnel must not disseminate information that is potentially unmasking to any masked personnel. The masked and unmasked site personnel must coordinate all study activities as necessary to protect masking and minimize bias during the study.

In the event of a medical emergency where the knowledge of subject treatment is required, an individual Investigator will have the ability to unmask the treatment assignment for a specific subject after contacting an appropriate Study Sponsor representative if time allows.

Unmasking must be done according to the instructions provided for the study IRT system.

Refer to Section 11.5.

